**10.3.4.13. Vital Signs**

Vital signs will be listed for all randomized patients.

Descriptive statistics for the actual measurements and changes from baseline for SBP and DBP, and PR will be presented by treatment and visit.

Vital signs will be analyzed using a similar MMRM-based model as that described in Section 10.3.1 for continuous variable analysis.

#### **10.3.4.14. Electrocardiograms**

Descriptive statistics for the absolute measurements, outliers, and changes from baseline for selected ECG parameters defined in the SAP, including QT corrected for heart rate using Fridericia's formula (QTcF) will be presented by treatment and visit. These parameters will be analyzed using a similar MMRM-based model as that described in Section 10.3.1 for continuous variable analysis.

#### **10.3.5. Pharmacokinetic/Pharmacodynamic Analyses**

Population PK analyses will be conducted using dosing data and dulaglutide concentrations obtained from all patients via commonly accepted pharmacostatistical methods (for example, nonlinear mixed-effects modeling), and covariate screening.

The relationship between dulaglutide doses and/or concentrations and key safety measures (such as QT intervals, BP and HR, nausea, vomiting), and efficacy measures (such as fasting glucose, HbA1c, and weight) will be assessed in PK/PD analyses. Endpoints may include but are not necessarily limited to those listed above.

In addition, if positive antibody titers to dulaglutide are observed, the relationship between dulaglutide PK concentrations and antibody formations will be evaluated for impact on dulaglutide clearance and, if applicable, drug effect(s).

#### **10.3.6. Subgroup Analyses**

Subgroup analyses of treatment interaction for important factors, including age, race, gender, country, duration of diabetes, baseline HbA1c (<8%, ≥8%), and BMI may be conducted for the primary endpoint of HbA1c.

These will be conducted using the MMRM with treatment, visit, subgroup, treatment-by-visit, treatment-by-subgroup, visit-by-subgroup, and treatment-by-visit-by-subgroup as fixed effects, and baseline as covariate. If the MMRM fails to converge, the corresponding analysis of covariance (ANCOVA) or ANOVA model (LOCF) will be used.

When analyzing baseline HbA1c as a subgroup, the baseline HbA1c will not be included as a covariate to avoid colinearity.

Other exploratory subgroup analyses may be performed as deemed appropriate.

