## **7.2. Method of Treatment Assignment**

Patients who meet all criteria for enrollment will be randomized to 1 of the study treatment arms at Visit 3. Assignment to treatment arms will be determined by a computer-generated random sequence using an IWRS. The IWRS will be used to assign cartons containing double-blind study drug to each patient. Site personnel will confirm that they have located the correct cartons by entering a confirmation number found on the label into the IWRS.

Block randomization will be used at the country level. Patients will be randomized in a 1:1:1:1 ratio (dulaglutide 4.5 mg, dulaglutide 3.0 mg, dulaglutide 1.5 mg, placebo). Within the dulaglutide 4.5 mg and 3.0 mg arms, patients will be randomly assigned (1:1) to Algorithm 1 or Algorithm 2. Randomization will be stratified by HbA1c (<8%, ≥8%).

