### 10.3. Statistical Analyses

#### 10.3.1. General Statistical Considerations

Statistical analysis of this study will be the responsibility of Lilly or its designee. Any change to the data analysis methods described in the protocol will require an amendment ONLY if it changes a principal feature of the protocol. Any other change to the data analysis methods described in the protocol, and the justification for making the change, will be described in the

clinical study report (CSR). Additional exploratory analyses of the data will be conducted as deemed appropriate.

Unless otherwise specified, listings will include all randomized patients. Efficacy and safety analyses will be conducted in the intent-to-treat (ITT) population. The primary efficacy measure (change from baseline in HbA1c) will also be evaluated in the PP population and Completer sets. In all efficacy and hypoglycemia analyses, all data after rescue therapy will be censored. Analyses of safety parameters, except for hypoglycemia events, will be conducted in the ITT population including the post-rescue therapy data.

Countries with fewer than 10 randomized patients will be pooled for statistical analyses. Pooled country will be employed for all formal statistical model-based analyses.

Unless otherwise specified, all tests of treatment effects will be conducted at a 2-sided alpha level of 0.05, and confidence intervals (CIs) will be calculated at 95%, 2-sided. All tests of interactions between treatments and factors of interest will be conducted at a 2-sided alpha level of 0.10.

The baseline visit will be Visit 3. For all variables, including HbA1c, if baseline data are not available or are missing, the last nonmissing measurement taken prior to this visit will be used for the baseline measurement. The measurement for the primary analysis is defined as the change from baseline in HbA1c to Week 18 (Visit 12).

For all statistical analyses, missing data will be treated as missing at random; therefore, no imputation is needed unless otherwise stated.

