The analysis of covariance (ANCOVA) as a sensitivity analysis for the primary and secondary continuous efficacy endpoints using the last observation carried forward (LOCF) described in Section 10.3.1 of the protocol H9X-MC-GBGJ(a) will not be used for analyses of secondary continuous efficacy endpoints as the analysis was shown to produce biased results (Lachin 2016) with little inferential value.

For continuous laboratory measurements for safety, an analysis of variance (ANOVA) on ranks will be used with treatment as a fixed effect.

For all continuous measures, summary statistics will include number of patients, mean, SD, median, minimum, and maximum for both the actual and change from baseline values at each scheduled visit for each treatment unless otherwise specified. Least-squares mean (LS mean) and standard errors (SEs) derived from the model will also be displayed for the change from baseline values at each scheduled visit for each treatment. Treatment comparisons will be displayed showing the treatment difference LS mean and the 95% CIs between each dose and placebo, and between each investigational dulaglutide dose and 1.5 mg at the same visit, along with the corresponding p-values.

Summary statistics for categorical measures will include number of subjects and percentages. The percentage of patients achieving target HbA1c <7.0% at Week 18 will be analyzed using a longitudinal logistic regression with repeated measurements with treatment, visit, treatment-by-visit interaction, and baseline HbA1c-by-visit interaction as fixed effects and baseline HbA1c as a covariate. For the analysis of other categorical measures, Fisher's exact test will be used for treatment comparisons, unless 80% of cells have an expected value of at least 5, in which case the Chi-square test will be used unless otherwise stated. Unless otherwise stated, categorical variables will be summarized by sample size, the number of patients and percentages for each treatment group at each visit.

Imputed data may be applied in model-based data analysis, but will not be used in data listing.

The latter will only present the non-imputed raw data including site reported scheduled, site reported unscheduled, or early termination visit data; however, only scheduled visits for the measure of interest ([Appendix 1](#), Table APP1.1) will be included in the summary table and statistical inference unless otherwise stated.

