6.14. Subgroup Analyses

Subgroup analyses of the treatment interaction for important factors, including age group, race, gender, country, duration of diabetes ($<$ median, \geq median), baseline HbA1c ($< 8\%$, $\geq 8\%$), and BMI ($<$ median, \geq median), may be conducted for the primary endpoint of HbA1c. Country will use the pooled country.

These will be conducted using the MMRM with treatment, visit, subgroup, treatment-by-visit, treatment-by-subgroup, visit-by-subgroup, and treatment-by-visit-by-subgroup as fixed effects, and baseline as a covariate. If the MMRM fails to converge, the corresponding analysis of covariance (ANCOVA) or ANOVA model (LOCF) will be used.

When analyzing baseline HbA1c as a subgroup, the baseline HbA1c will not be included as a covariate to avoid colinearity.

TEAE exceeding 5% will be summarized descriptively for the patients with the top quartile of the body weight reduction from baseline by treatment group.

Other exploratory subgroup analyses may be performed as deemed appropriate.

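### The optional HbA1c subgroup model lists no pooled country term, falls back to LOCF on non-convergence, and does not say which contrast is the interaction test (minor)

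*Protocol*

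**What the plan says.** Protocol 10.3.6 describes subgroup analyses by age, race, gender, country, duration of diabetes, baseline HbA1c and BMI. They are optional: the list of factors ends "BMI may be conducted for the primary endpoint of HbA1c". Protocol 10.3.1 defines that endpoint as the change from baseline to Week 18 (Visit 12).

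The model is stated as: "These will be conducted using the MMRM with treatment, visit, subgroup, treatment-by-visit, treatment-by-subgroup, visit-by-subgroup, and treatment-by-visit-by-subgroup as fixed effects, and baseline as covariate". SAP 6.14 has the same terms, ending "treatment-by-subgroup, visit-by-subgroup, and treatment-by-visit-by-subgroup as fixed effects, and baseline as a covariate". It mentions pooled country only as the form in which country enters when country is itself the subgroup.

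The general rule in Protocol 10.3.1 is: "Pooled country will be employed for all formal statistical model-based analyses". SAP 6.1 repeats it as a block factor, but allows for exceptions that are denoted elsewhere. Protocol 7.2 gives the reason for the term: "Block randomization will be used at the country level".

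On non-convergence the subgroup text says: "If the MMRM fails to converge, the corresponding analysis of covariance (ANCOVA) or ANOVA model (LOCF) will be used". For the MMRM in general, Protocol 10.3.1 and SAP 6.1 instead give an ordered list of simpler covariance structures. SAP 6.1 also says that an LOCF-based ANCOVA "will not be used for analyses of secondary continuous efficacy endpoints as the analysis was shown to produce biased results".

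Both documents set a two-sided alpha of 0.10 for interaction tests. Neither says which term or contrast of the subgroup model is that test, or at which visit it is read.

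**The concern.** Read literally, the subgroup model differs from the primary model in two ways. It leaves out the randomization block, so subgroup estimates would come from a model adjusted differently from the primary one. Its fallback carries forward early HbA1c values, a method that the SAP calls biased when it withdraws it for other continuous efficacy endpoints.

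The unnamed interaction test is a separate gap. With the three-way term in the model, a default Type III test of treatment-by-subgroup gives equal weight to each modelled visit, and the visits are not interchangeable. By Table GBGJ.2 the maintenance dose starts at Week 6. At the Week 6 sample the 4.5 mg arm has therefore received at most 3.0 mg (Algorithm 1) or 1.5 mg (Algorithm 2), and the 3.0 mg Algorithm 2 group at most 1.5 mg. HbA1c is also drawn at Week 22, after treatment, and nothing says whether that value enters the model.

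What is at stake is how clearly an exploratory subgroup finding can be read, and whether the test is fixed before unblinding. The trial is meant to guide Phase 3 design, so such findings may be used.

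**Working it through.** **The plan's own figure.** The documents give no power for subgroups. For the main comparison (difference 1.0%, SD 1.2%, 60 completers per arm, two-sided alpha 0.05), SE = 1.2 × √(2/60) = 0.219. Then 1.0/0.219 − 1.96 = 2.60, which is 99.5% power. The stated floor of 90% is met.

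**Interaction SE.** Take one dose against placebo and a two-level subgroup, assumed to split 50/50, so 30 completers per cell. At Week 18, SE = 1.2 × √(4/30) = 0.438.

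**1. Leaving out pooled country.** If country explains a share R² of the variance and arms are balanced within country, omission multiplies the SE by about 1/√(1 − R²), less the small cost of estimating the country terms. I simulated Week 18 data with 300 patients, 8 countries, blocked 1:1:1:1 allocation and 20% missing. The number of countries and R² are assumptions.

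| R² | 1/√(1 − R²) | simulated SE ratio, without/with country |
|---|---|---|
| 2% | 1.010 | 0.995 |
| 5% | 1.026 | 1.01 |
| 10% | 1.054 | 1.04 |

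The range is about 0% to 5%. At most, 0.438 becomes 0.438 × 1.05 = 0.460.

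**2. LOCF fallback.** Use the onset form of SAP 6.11.2.3, f(t) = (1 − e^(−kt))/(1 − e^(−18k)), with k assumed to be 0.05 to 0.2 per week. Dropout is assumed uniform over 18 weeks, and patients who leave before Week 6 have no value to carry. For total dropout d, a 1% effect shrinks by [d × 4/18 × (1 − f(6)) + d × 8/18 × (1 − f(10))] / (1 − d × 6/18).

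- k = 0.2, d = 20%: f(6) = 0.718 and f(10) = 0.889, so (0.0444 × 0.282 + 0.0889 × 0.111)/0.933 = 0.02.
- k = 0.05, d = 30%: f(6) = 0.437 and f(10) = 0.663, so (0.0667 × 0.563 + 0.1333 × 0.337)/0.90 = 0.09.

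These figures are for a treatment effect. An interaction that followed the same curve would shrink by the same proportion, 2% to 9%.

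The fallback should seldom be needed. With three on-treatment HbA1c visits, an unstructured covariance has 3 × 4/2 = 6 parameters, for about 300 patients.

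**3. Which interaction is tested.** I fitted the listed terms to data built with interactions of 0.1, 0.5 and 0.9 at Weeks 6, 10 and 18. Under sum-to-zero coding (the Type III test) the treatment-by-subgroup term is (0.1 + 0.5 + 0.9)/3 = 0.50. With Week 18 as the reference visit, the same term is 0.90. The model is saturated in treatment, visit and subgroup, so the Week 18 value is available by a contrast without changing the model.

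For power at alpha 0.10, assume a true Week 18 interaction of 0.8%, equal SDs at each visit and between-visit correlation ρ of 0.5 to 0.9. The SE of the average is 0.438 × √((1 + 2ρ)/3), which is 0.358 to 0.423.

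| Interaction at Weeks 6/10/18, relative to Week 18 | averaged estimate | power, averaged test | power, Week 18 contrast |
|---|---|---|---|
| 1 / 1 / 1 | 0.80 | 60–72% | 57% |
| 0.5 / 0.8 / 1 | 0.61 | 42–53% | 57% |
| 0 / 0.5 / 1 | 0.40 | 25–30% | 57% |

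Averaging gains power when the interaction is constant over visits and loses it when the interaction builds up.

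**The case against.** **Country.** The general rule already covers this model, and SAP 6.14 does not expressly make an exception. SAP term lists are not always complete: SAP 6.1 lists the HbA1c-target model without pooled country, and SAP 6.11.3.1 refers to that same model and includes it. This stands in part. The general rule may be meant to apply, but nothing in 10.3.6 or 6.14 says so, and a programmer working from the list would leave the term out.

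**Fallback.** References to the MMRM can be read as carrying its covariance sequence with them, which makes LOCF a last resort. The SAP's withdrawal of LOCF ANCOVA is worded for secondary endpoints, and SAP 6.17 keeps LOCF for non-longitudinal variables. This too stands in part. Even as a last resort, LOCF for a longitudinal HbA1c endpoint fits badly with the SAP's stated reason for rejecting it elsewhere.

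**Interaction test.** A reader might infer that the plan tests an interaction averaged over visits and so misses its endpoint. The documents do not support that. They never name the treatment-by-subgroup main term as the test, they tie the analysis to an endpoint fixed at Week 18, and Protocol 10.3.1 displays treatment comparisons visit by visit. The three-way term makes the Week 18 interaction estimable. This objection stands: what remains is an unnamed contrast.

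**Weight.** The analyses are optional, SAP 6.5 calls the study exploratory, and neither the primary analysis nor the interim HbA1c criterion uses this model. This stands, and it sets the severity.

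**Conclusion.** Minor. On the text, pooled country is missing from the listed terms against the Protocol's unqualified rule, and the written fallback is LOCF with no reference to the covariance sequence. The SAP's exception clause and its other incomplete lists leave room for the general rule to fill the first gap.

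The effects are small: about 0% to 5% on the interaction SE, and 0.02 to 0.09 points on a 1% effect in the unlikely event that LOCF is reached. Both rest on assumptions that are not in the documents (number of countries, country variance, onset rate, dropout pattern).

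The interaction test is a matter of clarification. The stronger conclusions, that the plan targets the wrong endpoint or that its subgroup test systematically loses power, do not follow. Bias toward zero arises only if the early interaction is smaller than the one at Week 18.

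**What to change.** In Protocol 10.3.6 and SAP 6.14:

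1. Add pooled country as a fixed effect, except where country is the subgroup.
2. On non-convergence, apply the covariance sequence of Protocol 10.3.1 and SAP 6.1 first. If every structure fails, fit ANCOVA to observed Week 18 values instead of LOCF (ANOVA where baseline HbA1c is the subgroup, since the covariate is then dropped).
3. As a clarification, state that the interaction is read at alpha 0.10 from the Week 18 (Visit 12) treatment-by-subgroup contrast, with on-treatment visits only in the model.

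The cost is a few lines of wording and one contrast statement per factor. No new data are needed. The Week 18 test may be somewhat less powerful than the averaged one when the interaction is constant over visits (57% against 60–72% in the example above), and an observed-value ANCOVA uses fewer patients than LOCF. Both are acceptable for a test that matches the endpoint.

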#### **10.3.7. Interim Analyses**

There will be at least 3 interim safety analyses for this study. The purpose of these analyses will be to monitor the safety and tolerability of the 2 investigational dulaglutide doses. An additional interim efficacy/safety analysis may be conducted for sponsor planning purposes. An AC will be formed to review the interim analyses in an unblinded fashion. The first interim safety analysis will occur after approximately 15 patients have completed 8 weeks of treatment. The AC will continue to evaluate safety when approximately 30 and 60 patients have exposure to therapy for

at least 8 weeks (interim safety analyses 2, and 3, respectively). The efficacy/safety interim analysis will be conducted after approximately 120 patients have completed the 18-week therapy. The AC proceedings will be described in a separate AC charter. Any change to the proceedings will be included in the AC charter and will not require a protocol amendment.

Only the AC and Statistical Analysis Center will be authorized to evaluate unblinded interim analyses. Study sites will receive information about interim results ONLY if they need to know for the safety of their patients.

Unblinding details are specified in the unblinding plan section of the statistical analysis plan (SAP).

#### **10.3.7.1. PK/PD Prelock Data Access**

A limited number of preidentified individuals will require access to the unblinded PK and PD (safety and efficacy) data, as specified in the unblinding plan, prior to final database lock. This is necessary in order to initiate population PK/PD model development for final analyses.

Information that may unblind the study during the analyses will not be reported to study sites or to the blinded study team until the study data lock occurs.

## 12. Appendices

---

## Appendix 1. Abbreviations and Definitions

---

Term	Definition
AC	Assessment Committee
ADA	anti-drug antibodies
AE	adverse event: Any untoward medical occurrence in a patient or clinical investigation subject administered a pharmaceutical product that does not necessarily have a causal relationship with this treatment. An adverse event can therefore be any unfavorable and unintended sign (including an abnormal laboratory finding), symptom, or disease temporally associated with the use of a medicinal (investigational) product, whether or not related to the medicinal (investigational) product.
ALT	alanine aminotransferase
ANCOVA	analysis of covariance
ANOVA	analysis of variance
AST	aspartate aminotransferase
blinding/masking	
A single-blind study is one in which the investigator and/or his staff are aware of the treatment but the patient is not, or vice versa, or when the sponsor is aware of the treatment but the investigator and/his staff and the patient are not.
 
A double-blind study is one in which neither the patient nor any of the investigator or sponsor staff who are involved in the treatment or clinical evaluation of the patients are aware of the treatment received.

BMI	body mass index
BP	blood pressure
bpm	beats per minute
CI	confidence interval
CKD-EPI	Chronic Kidney Disease-Epidemiology
Complaint	A complaint is any written, electronic, or oral communication that alleges deficiencies related to the identity, quality, purity, durability, reliability, safety or effectiveness, or performance of a drug or drug delivery system.
CRP	clinical research physician: Individual responsible for the medical conduct of the study. Responsibilities of the CRP may be performed by a physician, clinical research scientist, global safety physician, or other medical officer.
CSR	clinical study report

CT	computed tomography
CV	cardiovascular
DBP	diastolic blood pressure
DPP-4	dipeptidyl peptidase-4
ECG	electrocardiogram
eCRF	electronic case report form
eGFR	estimated glomerular filtration rate
Enroll	The act of assigning a patient to a treatment. Patients who are enrolled in the trial are those who have been assigned to a treatment.
Enter	Patients entered into a trial are those who sign the informed consent form directly or through their legally acceptable representatives.
ERB	Ethics Review Board
ET	early termination
FPG	fasting plasma glucose
GCP	good clinical practice
GI	gastrointestinal
GLP-1	glucagon-like peptide-1
GLP-1 RA	glucagon-like peptide-1 receptor agonist
HbA1c	hemoglobin A1c
HOMA	Homeostasis Model Assessment
HOMA-%B	$\beta$ -cell function as measured by the HOMA2 method
HOMA-IR	insulin resistance as measured by the HOMA2 method
HR	heart rate
IB	Investigator's Brochure
ICF	informed consent form
ICH	International Conference on Harmonisation
interim analysis	An interim analysis is an analysis of clinical study data, separated into treatment groups, that is conducted before the final reporting database is created/locked.

investigational product	A pharmaceutical form of an active ingredient or placebo being tested or used as a reference in a clinical trial, including products already on the market when used or assembled (formulated or packaged) in a way different from the authorized form, or marketed products used for an unauthorized indication, or marketed products used to gain further information about the authorized form.
ITP	integrated 2-component prediction
ITT	intention to treat: The principle that asserts that the effect of a treatment policy can be best assessed by evaluating on the basis of the intention to treat a patient (that is, the planned treatment regimen) rather than the actual treatment given. It has the consequence that patients allocated to a treatment group should be followed up, assessed, and analyzed as members of that group irrespective of their compliance to the planned course of treatment.
IWRS	interactive web-response system
LOCF	last observation carried forward
LS mean	least-squares mean
MedDRA	Medical Dictionary for Regulatory Activities
MI	myocardial infarction
MMRM	mixed-model repeated measures
MRI	magnetic resonance imaging
MTC	medullary thyroid carcinoma
NAFLD	nonalcoholic fatty liver disease
NOAEL	no adverse effect level
OAM	oral antihyperglycemia medications
OTC	over-the-counter
PD	pharmacodynamic
PFS	prefilled syringe
PG	plasma glucose
PK	pharmacokinetics
PP	per-protocol set: The set of data generated by the subset of patients who sufficiently complied with the protocol to ensure that these data would be likely to exhibit the effects of treatment, according to the underlying scientific model.
PR	pulse rate
QTc	corrected QT interval

SAE	serious adverse event
SAP	statistical analysis plan
SBP	systolic blood pressure
Screen	The act of determining if an individual meets minimum requirements to become part of a pool of potential candidates for participation in a clinical study.
SD	standard deviation
SE	standard error
SmPC	Summary of Product Characteristics
SMPG	self-monitored plasma glucose
SUSARs	suspected unexpected serious adverse reactions
T1D	type 1 diabetes
T2D	type 2 diabetes
TEAE	treatment-emergent adverse event: An untoward medical occurrence that emerges during a defined treatment period, having been absent pretreatment, or worsens relative to the pretreatment state, and does not necessarily have to have a causal relationship with this treatment.
ULN	upper limit of normal
US	United States
USPI	United States Package Insert
WHO	World Health Organization

---

---

